7.1.1.3 Disease-Related Signs and Symptoms

Patient-reported disease-related symptoms as assessed by the validated PRO instrument MPN-SAF TSS 2.0 (Appendix 5) will be collected daily using an electronic diary and will be evaluated as a part of the dose–response relationship. Patients must begin reporting symptoms via electronic diary at least 7 days before starting pacritinib treatment and will continue until the Week 48 visit. After Week 48, the patient will fill out the questionnaire (Appendix 3) at each follow up visit. The questionnaire is the same PRO instrument and uses a 7 day recall period. The MPN-SAF TSS 2.0 will be translated and available on the eDiary device in several different languages to accommodate an international study.

In addition, the patient global impression assessment questionnaire (Appendix 11) will be completed at the end of Week 12, the end of Week 24 or the end of treatment visit, and every 3 months up to 2.5 years.

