Appendix 11 - Patient Global Impression Assessment

Patient Global Impression Assessment

Patient Number: Today's date (day/month/year): / /

Instructions: Circle the answer that is most appropriate.

Since the start of the treatment you've received in 1. Very much improved this study, your myelofibrosis symptoms are:

- 2. Much improved
- 3. Minimally improved
- 4. No change
- 5. Minimally worse
- 6. Much worse
- 7. Very much worse

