10.3 Patient Global Impression Assessment

The self-reported measure Patient Global Impression of Change (PGIC) is a 7 point scale depicting a patient's rating of overall improvement. Patients rate their change as 'very much improved', 'much improved', 'minimally improved', 'no change', 'minimally worse' or 'very much worse'. PGIC will be collected at the end of Week 12, the end of Week 24 or the end of treatment visit and every 3 months up to 2.5 years.

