12 EFFICACY ENPOINTS AND ANALYSES

12.1 PRIMARY EFFICACY ENPOINTS

12.1 1 Spleen Volume Reduction

The primary efficacy variable for dosage selection is the percent reduction in spleen volume from baseline as measured by MRI or CT at Weeks 12 and 24..

Descriptive statistics of spleen volume at baseline, Week 12, Week 24, and at End of Treatment will be presented by treatment arm. Spleen volume at End of Treatment is defined as the spleen volume collected at the end of treatment visit or the last spleen volume measured on treatment if not measured at end of treatment. Descriptive statistics of percent reduction in spleen volume at Weeks 12 and 24 and at End of Treatment will be presented by treatment arm. These descriptive statistics include counts, mean, standard deviation, standard error of the mean, median, 25th percentile, 75th percentile, minimum, and maximum. As a supportive measure of efficacy, the counts and proportions of patients with spleen volume reduction (SVR) $\geq 35\%$ at Weeks 12 and 24 and at End of Treatment will be presented by treatment arm. The exact (Clopper-Pearson) 95% confidence intervals (CIs) for the proportions will also be presented. Additional supportive analyses include imputing missing Week 24 spleen volume with the previous post-baseline (Week 12) spleen volume, if any, and repeating the above analyses. These analyses will be repeated for spleen volume measured after Week 24 in long term follow up.

12.1 2 Total Symptom Score (TSS) Analysis

Descriptive statistics of individual symptoms and TSS at baseline, every 12 weeks, and at End of Treatment will be presented by treatment arm. Descriptive statistics of percent reduction in TSS every 12 weeks and at End of Treatment will be presented by treatment arm. The counts and proportions (including Clopper-Pearson 95% CIs) of patients with TSS reduction $\geq 50\%$ every 12 weeks and at End of Treatment will be presented by treatment arm. Supportive analyses include imputing missing Week 24 TSS with the previous post-baseline (Week 12) TSS, if any, and repeating the above analyses at Week 24.

As an anchor for patient-reported symptom assessment, the patient global impression assessment (PGIA) will also be summarized and evaluated for correlation with TSS. There is 1 domain in the PGIA instrument with possible scores ranging from 1 (very much improved) to 7 (very much worse).

12.1 3 Patient Global Impression Assessment

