The scores for the PGIA will be summarized by treatment arm at each visit at which the patients are scheduled to complete the instrument using descriptive statistics. Additionally, the correlation between PGIA and TSS and the change in PGIA and change in TSS at each visit assessed will be explored.

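### The SAP's anchor analysis uses a change in the global impression rating, which has no baseline to change from, and does not name the matching pairing: rating against TSS change from baseline

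*SAP*

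**What the plan says.** SAP 12.1.2 gives the PGIA its role: "As an anchor for patient-reported symptom assessment, the patient global impression assessment (PGIA) will also be summarized and evaluated for correlation with TSS". SAP 12.1.3 then sets out the analysis: "the correlation between PGIA and TSS and the change in PGIA and change in TSS at each visit assessed will be explored". Two pairings are named, PGIA with TSS and change in PGIA with change in TSS, both at every visit assessed.

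The instrument is described in three places.

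- **Protocol Appendix 11.** The single item begins "Since the start of the treatment you've received in" this study and asks how the patient's myelofibrosis symptoms now are. There are seven answers, from the greatest improvement (1) to the greatest worsening (7).
- **SAP 10.3.** "The self-reported measure Patient Global Impression of Change (PGIC) is a 7 point scale depicting a patient's rating of overall improvement". On timing, "PGIC will be collected at the end of Week 12, the end of Week 24 or the end of treatment visit", and every three months after that.
- **Protocol 7.1.1.3.** The questionnaire "will be completed at the end of Week 12, the end of Week 24 or the end of treatment visit", and then every three months. Protocol Table 1 agrees: its PGIA row is marked at Week 12, Week 24, post-Week-24 follow-up and End of Treatment, and nowhere earlier.

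For the TSS, SAP 10.2 defines a baseline (the mean over the seven days before treatment) and derives percent reduction from it.

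**The concern.** An anchor analysis asks whether movement in a symptom score agrees with the patient's own view of how much they have changed. The natural comparison sets the change rating beside the change in score over the same period. The SAP names two other comparisons. One sets a change rating beside the current symptom level. The other calls for a change in something that is already a change and was never recorded at baseline.

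If the sentence is followed literally, part of it cannot be carried out and the rest answers a different question. SAP section 1 says that analyses added to those planned will be labelled post hoc. If the matching comparison is supplied only at reporting, it would carry that label, although the PGIA is the only anchor the SAP plans for the TSS.

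**Working it through.** The plan attaches no numerical figure to this analysis, so there is none to reproduce. The check is first textual, then illustrative.

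**1. What can be computed at each visit**

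| Quantity | Week 12 | Week 24 and later |
|---|---|---|
| PGIA score (change since start of treatment) | yes | yes |
| TSS level | yes | yes |
| TSS change from baseline | yes | yes |
| PGIA change from baseline | no: no baseline rating | no: no baseline rating |
| PGIA difference from an earlier visit | no, when Week 12 is the first rating | yes, but undefined in the SAP |

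A patient who stops treatment before Week 12 may have an earlier End of Treatment rating; for all others Week 12 is the first scheduled rating. From Week 24 a between-visit PGIA difference covers the interval between those visits, whereas TSS change from baseline covers the whole period since the start of treatment. Unless both are taken over the same interval, the two do not match.

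**2. Rating against TSS level: absolute change**

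The documents give no TSS standard deviations or correlations, so the inputs here are assumptions. Let v be the ratio of the visit SD to the baseline SD, and ρ the correlation of baseline with visit TSS. Scale the baseline SD to 1. Then Cov(change, level) = v² − ρv and Var(change) = 1 + v² − 2ρv, so

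corr(change, level) = (v − ρ) / √(1 + v² − 2ρv).

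This is the correlation a rating would show with TSS level if it tracked absolute TSS change perfectly and linearly.

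| v | ρ = 0.3 | ρ = 0.5 | ρ = 0.7 |
|---|---|---|---|
| 0.8 | 0.46 | 0.33 | 0.14 |
| 1.0 | 0.59 | 0.50 | 0.39 |
| 1.2 | 0.69 | 0.63 | 0.57 |

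For example, v = 0.8 and ρ = 0.7 give 0.1/√0.52 = 0.14; v = 1.2 and ρ = 0.3 give 0.9/√1.72 = 0.69. With equal SDs the formula reduces to √((1 − ρ)/2).

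**3. Rating against TSS level: percent change**

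Percent change is the variable the SAP derives, and the formula above does not cover it. A simulation assumed normal TSS, patients kept only if baseline TSS was at least 10 (one of the entry routes in inclusion criterion 5), a Week 24 mean 20% below the untruncated baseline mean, scores floored at 0, equal SDs, and a correlation of 0.5 to 0.7 before truncation. With baseline mean and SD of 20 and 10, or 25 and 12, the Spearman correlation of Week 24 level with percent change is 0.67 to 0.77. Crossing those means and SDs (20 with 12, 25 with 10) widens the range to 0.65 to 0.79.

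**4. A noisy seven-point rating**

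A second simulation used equal SDs, the same correlation ρ between all pairs of visits (0.3, 0.5 or 0.7), a mean fall of 0.4 SD at both visits, and a rating made of absolute TSS change plus noise of the same SD, cut into seven categories.

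| Pairing at Week 24 | Correlation |
|---|---|
| PGIA score with TSS change from baseline | 0.68 to 0.69 |
| PGIA score with TSS level | 0.41, 0.34, 0.27 (ρ = 0.3, 0.5, 0.7) |
| PGIA difference, Weeks 12 to 24, with TSS change from baseline | 0.28 |
| PGIA difference with TSS difference, both Weeks 12 to 24 | 0.55 to 0.56 |

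**The case against.** The strongest reply is that this is loose drafting. SAP 10.3 calls the instrument an impression of change, so the authors may have meant the rating itself when they wrote of a change in PGIA. Likewise, the correlation with TSS promised in SAP 12.1.2 sits in a section that analyses both TSS level and percent reduction. That reading is possible, but SAP 12.1.3 names PGIA and change in PGIA as separate quantities, so a programmer following the text would not arrive at it. The wording still needs correcting.

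Two further replies stand in full. PGIA against TSS level can be computed; it is a mismatched anchor, not an impossible one. A between-visit PGIA difference, paired with the TSS difference over the same interval, is also a legitimate analysis from Week 24 on, once it is defined.

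A reader might go further and infer that the flaw undermines the TSS evidence used in dose selection. The documents do not support that. The efficacy variables for dose selection in Protocol 11.1 and SAP section 10 are percent spleen volume reduction, the 35% spleen response, percent TSS reduction and the 50% TSS response. The PGIA is not among them; Protocol 11.1 lists it only under long-term efficacy. The 50% threshold is fixed in advance and not derived from the PGIA, the protocol describes the TSS instrument as validated, and there is no hypothesis test.

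A reader might also infer that the anchor must look weak, at about 0.39 to 0.50, even if it worked perfectly. Those values are the equal-SD figures for absolute change at ρ of 0.7 and 0.5. Other SD ratios give anything from 0.14 to 0.69, and percent change gives higher values.

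**Conclusion.** The point holds as a defect in one exploratory sentence. It is certain from the text that the PGIA is a since-start-of-treatment change rating, that no baseline rating is scheduled, that change in PGIA is undefined and cannot be formed at Week 12 when that is the first rating, and that PGIA score against TSS change from baseline is not named.

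The numerical effect is not certain. Pairing the rating with TSS level weakens the anchor correlation, by an amount that depends on TSS variability the documents do not report. With perfect tracking, the ceiling is about 0.14 to 0.69 for absolute change (SD ratios 0.8 to 1.2, ρ 0.3 to 0.7) and about 0.67 to 0.77 for percent change under one plausible set of assumptions. The spleen volume analysis, the TSS analyses themselves and the choice of dose are unaffected. It is a minor correction, but worth making before the data are analysed.

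**What to change.** Replace the correlation sentence in SAP 12.1.3 with text such as:

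> At each visit at which both are assessed (Weeks 12 and 24, End of Treatment and later visits), the Spearman correlation of the PGIA score with the change and percent change in TSS from baseline to that visit will be explored, and TSS change will be summarised by PGIA category.

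Delete change in PGIA, or define it as a between-visit difference paired with the TSS difference over the same interval. Keep all visits, since the protocol lists the PGIA as a long-term efficacy measure. State the expected sign: a higher PGIA score means worse, so it should correlate positively with TSS change and negatively with TSS percent reduction.

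In the same edit, correct SAP 10.3, which describes a seven-point scale but lists six categories; the sixth point in Appendix 11, much worse, is missing. Use one name for the instrument throughout.

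The cost is a few lines of SAP text. No new data are needed, and the TSS baseline and percent reduction are already derived.

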12.2 EXPLORATORY EFFICACY ANALYSIS

12.2 1 Spleen Length Reduction

Descriptive statistics of spleen length by physical exam at each visit will be presented by treatment arm. Descriptive statistics of percent reduction in spleen length at each post-baseline visit will be presented by treatment arm. The counts and proportions (including Clopper-Pearson 95% CIs) of patients with spleen length reduction $\geq 50\%$ at Weeks 12 and 24 will be presented by treatment arm.

12.2 2 Transfusions

The change in the frequency of transfusions will be summarized by treatment arm over time using descriptive statistics in patients receiving at least one transfusion at baseline or while on study treatment. This summary is dependent on the number of patients who received at least one transfusion at baseline or while on study treatment.

12.2 3 ECOG Performance Status

The scores for the ECOG performance status will be summarized by treatment arm at each visit using descriptive statistics such as counts and percent. In addition, the shift from baseline to worst ECOG performance status at post-baseline visits will be presented by treatment arm.

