7.1.1.4 Other Assessments

Patients will be followed for leukemic transformation and frequency of RBC and platelet transfusions. DNA samples will also be collected for analysis of mutations associated with myelofibrosis at baseline and Week 24.

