5. ANALYSIS POPULATIONS AND APPROACHES TO ANALYSIS

5.1 FULL ANALYSIS SET

The full analysis set (FAS) is defined as all randomized patients who received at least one dose of study treatment. Patients in this population will be analyzed according to the treatment arm to which they were assigned at randomization. The FAS will serve as the population for the analyses of efficacy, in keeping with the intent-to-treat (ITT) principle. Analyses of efficacy will provide an indication of potential benefit in the exploration to determine the recommended dose of pacritinib for further clinical studies.

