6. GENERAL STATISTICAL CONSIDERATIONS

6.1 DATA ANALYSIS CONVENTIONS

All data analysis will be performed by CTI or designee after the study is completed and the database has been locked and released. Statistical programming and analyses will be performed using SAS® version 9.4. Outputs will be provided in both RTF and PDF for tables, listings and figures using landscape orientation. Applicable study data will be listed at minimum by subject, treatment arm, and visit (as applicable) based on the analysis population as specified in this plan.

Summaries for continuous and ordinal variables will include the number of observations (n), arithmetic mean, standard deviation (SD), minimum, first quartile (Q1), median, third quartile (Q3), and maximum. Summaries of discrete variables will include frequency counts and percentages.

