10. EFFICACY VARIABLES

The primary efficacy variable for dosage selection is the percent reduction in spleen volume from baseline as measured by MRI or CT at Weeks 12 and 24.

Other supportive measures for evaluation as part of the dose-response relationship include

- the percentage of patients who achieve at least 35% reduction in spleen volume
- % TSS reduction from baseline, and
- the percentage of patients with at least 50% reduction in TSS.

The planned analyses for the efficacy endpoints of the study are detailed in the subsections below and will be performed in the full analysis set.

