10.5 Transfusions

10.6.1 Frequency of Red Blood Cell (RBC) Transfusions

The frequency of RBC transfusions at baseline is defined as the number of units of RBC transfusions per month prior to and including the date of the start of treatment. Since this data comes from two different sources, the baseline RBC transfusion frequency is computed as the sum of the number of units of RBC transfusions in the 90 days prior to the informed consent date and the number of units of RBC transfusions after the informed consent date through to the start of treatment date, divided by the number of days from informed consent to the start of treatment plus 90 days, multiplied by a conversion factor of 30 days/month. That is,

$$\frac{(\# \text{ units from Transfusion History} + \# \text{ units from IC to start of treatment})}{(90 + (\text{treatment start date} - \text{IC date} + 1)) \text{ days}} \times 30 \frac{\text{days}}{\text{month}}.$$

At post-baseline timepoints, the frequency of RBC transfusions is defined as the number of units of RBC transfusions per month in the three months (approximately 84 – 90 days) preceding the visit date. That is,

$$\frac{(\# \text{ units in the days preceding the visit date})}{\text{number of study days from previous visit}} \times 30 \frac{\text{days}}{\text{month}}$$

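### SAP 12.2.2 summarises change in transfusion frequency in a set partly defined by on-treatment transfusion, so arm means can mislead between doses, and no planned analysis counts new starters

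*SAP*

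**What the plan says.** SAP 12.2.2, under exploratory efficacy, has the change in transfusion frequency "summarized by treatment arm over time using descriptive statistics in patients receiving at least one transfusion at baseline or while on study treatment". It adds: "This summary is dependent on the number of patients who received at least one transfusion at baseline or while on study treatment".

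The general rule is wider. SAP section 10 says the efficacy analyses "will be performed in the full analysis set", which SAP 5.1 defines as "all randomized patients who received at least one dose of study treatment". SAP 5.1 also states: "The FAS will serve as the population for the analyses of efficacy, in keeping with the intent-to-treat (ITT) principle".

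The outcome is a rate. After baseline, by SAP 10.6.1, "the frequency of RBC transfusions is defined as the number of units of RBC transfusions per month". A patient with no transfusion before or during treatment therefore has a defined change of zero.

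Protocol 7.1.1.4 says: "Patients will be followed for leukemic transformation and frequency of RBC and platelet transfusions". That sets no denominator for the analysis, but it does not limit follow-up to transfused patients either.

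Red cell and platelet transfusion dependence are defined in SAP 8.2, Tables 1 and 2, as baseline characteristics. I found no post-baseline use of them, no FAS-wide summary of transfusion change, and no count by arm of patients who newly start transfusions.

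**The concern.** The set joins two conditions. Being transfused at baseline is fixed before treatment. Being transfused on treatment is the outcome under study. Under the second condition a dose that makes more patients start transfusions enlarges its own denominator, and patients who stay free of transfusion drop out of the average. The mean then describes change per transfused patient, not the burden in the arm.

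This matters because the trial is there to choose a dose. Anaemia and thrombocytopenia enter the primary safety measure only at grade 4 or above on central laboratory values (SAP section 13), and a patient can start transfusions without reaching that grade. SAP 13.2 itself recognises that haemoglobin is strongly affected by transfusion. Its remedy is to look at haemoglobin in patients with no transfusion in the 90 days before consent or on study. New starters leave that analysis and enter the one in 12.2.2, so both sets are selected on the outcome, in opposite directions.

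**Working it through.** The plan states no figure for this summary, so there is none to reproduce. The check is an identity followed by illustrative cases.

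**Notation, per arm.** N = FAS size; nB = patients transfused at baseline, with mean change dB; nS = patients who start on treatment, with mean change dS > 0. All changes are in units/month.

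- Subset mean (SAP 12.2.2) = (nB·dB + nS·dS) / (nB + nS)
- FAS mean = (nB·dB + nS·dS) / N, because every excluded patient contributes zero
- Proportion newly transfused = nS / (N − nB)

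The subset mean can be rewritten as dB + [nS/(nB + nS)]·(dS − dB). With dB held fixed, more starters raise it if dS > dB, leave it unchanged if dS = dB, and lower it if dS < dB. The FAS mean rises by dS/N with every starter in all three situations.

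**Inputs.** N = 50 is the maximum per arm in Protocol 11.7. All transfusion figures are assumed.

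| Case | nB | dB | dS | nS (arm 1, arm 2) | Subset mean | FAS mean | Newly transfused |
|---|---|---|---|---|---|---|---|
| A | 10 | 0 | +2 | 4, 16 | 0.57, 1.23 | 0.16, 0.64 | 4/40, 16/40 |
| B | 0 | – | +2 | 4, 16 | 2.00, 2.00 | 0.16, 0.64 | 4/50, 16/50 |
| C | 20 | +1 | +1 | 0, 15 | 1.00, 1.00 | 0.40, 0.70 | 0/30, 15/30 |
| D | 20 | +1.5 | +1 | 0, 15 | 1.50, 1.29 | 0.60, 0.90 | 0/30, 15/30 |
| E | 20 | 0 | +1 | 0, 15 | 0.00, 0.43 | 0.00, 0.30 | 0/30, 15/30 |
| F | 20 | 0 in arm 1, −0.5 in arm 2 | +1 | 0, 10 | 0.00, 0.00 | 0.00, 0.00 | 0/30, 10/30 |

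- **A, relative attenuation.** Subset: 8/14 = 0.57 and 32/26 = 1.23, ratio 2.2. FAS: 8/50 = 0.16 and 32/50 = 0.64, ratio 4. The attenuation is in the ratio; the absolute gap is larger in the subset (1.23 − 0.57 = 0.66) than in the FAS (0.64 − 0.16 = 0.48).
- **B and C, levelling.** In C the subset gives 20/20 and 35/35, both 1.00, while the FAS gives 20/50 and 35/50.
- **D, reversal.** The subset falls from 30/20 = 1.50 to 45/35 = 1.29 as the FAS mean rises from 30/50 to 45/50.
- **E, no masking.** Starters raise the subset mean.
- **F, offsetting changes.** Arm 2 is (20 × −0.5 + 10 × 1)/30 = 0. The FAS mean ties as well, and only the proportion newly transfused separates the arms.

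**Arm size.** SAP section 16 gives a maximum of 35 per arm. With N = 35, nB = 14 and dB = dS = +1, the subset mean is 1.00 with 0 or 15 starters; the FAS mean is 14/35 = 0.40 and 29/35 = 0.83. The conclusion does not depend on which size applies.

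**The case against.** The strongest reply is that the table hides little. SAP 6.1 says: "Summaries for continuous and ordinal variables will include the number of observations (n), arithmetic mean". In case B a reader would see 2.0 with n = 16 beside 2.0 with n = 4. Excluded patients contribute exactly zero, so with complete visit data the FAS mean is the subset mean times n/N: in case A, 1.23 × 26/50 = 0.64. This stands. What n does not do is split the 26 into 10 prior users and 16 starters. Subtracting baseline counts taken from the SAP section 8 tables would need the same baseline period, the same patients (section 8 uses all randomised patients) and complete visits, and it is not a planned output.

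A reader might infer that the rule makes a dose that starts more patients on transfusion look the same as one that does not. The documents do not support that as a general result. A tie needs few or no baseline users, baseline users who change as much as starters, or offsetting changes between arms. Having no baseline users is implausible, because inclusion criterion 3b(i) admits patients who developed a red cell transfusion requirement on ruxolitinib. In cases A and E the subset mean points the right way.

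The stakes are also limited. The analysis is exploratory and untested, and transfusion frequency is not among the variables named for dose selection. Haematological toxicity is also reported through grade 4 laboratory events, grade shift tables and adverse events by arm. All of that stands, but none of it counts new starters.

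**Conclusion.** The point holds. One limb of the set is a post-randomisation outcome and departs from the SAP's own FAS rule. Depending on dB relative to dS, the arm means can attenuate, level or reverse a between-dose difference in transfusion burden, or can show it in the right direction. The size is unknown because the documents give no transfusion rates; the figures above show what is possible, not what to expect.

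Three stronger readings should be set aside. Equal means are not the expected result. The FAS mean is not lost, since it can be recovered from n when visit data are complete. And nothing here touches the primary efficacy variable or the primary safety measure. What remains is a descriptive table that can mislead a comparison between doses, and a missing count of new starters. It is worth correcting, mainly because the data are already collected.

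**What to change.** In SAP 12.2.2, for red cells and platelets separately and by arm:

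1. Summarise change in frequency in all FAS patients with data, with never-transfused patients counted as zero.
2. Add the proportion newly transfused on treatment among patients with no transfusion in the baseline period of SAP 10.6.1 and 10.6.2 (the 90 days before consent through the start of treatment).
3. Add the change among patients transfused in that baseline period.

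The present subset may stay as a secondary row; the gain comes from the fixed denominators, and case F shows that row 2 is needed even with the FAS mean.

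The cost is SAP wording, a stated definition of transfusion-free at baseline, and a few more table rows from data already collected. FAS medians and quartiles may be zero if most patients are never transfused, so the mean should be read together with row 2.
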